The study will be a repeated-measures design. We will calculate subject and group averages for each condition from data normalized to a gait cycle. The data analyzed will include: leg stiffness, peak vertical and horizontal ground reaction forces, stance time, leg swing time, metabolic costs, top speed, peak socket pressure, and maximum socket motion. We will use repeated measures analysis of variance (ANOVA) to compare each variable across all conditions. Any significant differences will be further analyzed with either a Tukey HSD or Newman-Keuls follow-up procedure. In the case of an unequal number of subjects, we will use a Sheffe follow-up procedure. We will use p < 0.05 as a criterion for determining statistical significance. All statistical analyses will be performed with JMPIN software (JMPIN, SAS Institute, Cary, NC).

Specific Aim 1. Subjects will complete six experimental sessions at the University of Colorado Locomotion Lab; each session on a separate day and requiring approximately two hours of time. During each experimental session, subjects will run at two speeds, the speed required for their age/sex 50th percentile PFT (Physical Fitness Test) 2 mile run and a standard speed of 3 m/s on a force measuring treadmill while we measure their ground reaction forces, metabolic demand, socket pressures, and socket pistoning. Subjects will run with three different brands (Ossur,

Ottobock, and Freedom Innovations) of distance-running RSPs with three different stiffnesses at one height and three different heights at one stiffness of each brand, a total of five or more different conditions per brand at two speeds. Individual trials will be five minutes long with at least 2 minutes rest between trials.

Day DR0: Subjects will be asked to give informed written consent and then will be fit and aligned by a certified prosthetist with three different distance-running RSP brands, one from each company. We will measure each subject's height, weight, and limb segment lengths. Then, we will select an RSP stiffness category based on the subject's weight and manufacturer's recommendation. An appropriate RSP height for each subject will be chosen according to conventional practice. Our prosthetist will ensure that the prosthetic fit and alignment are adequate. Then, subjects will have time to accommodate to treadmill running with each distance-running RSP.

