Day DR1: We will first vary the distance-running RSP stiffness (k) while keeping height (h) at the traditionally recommended level. Subjects will use an RSP with the manufacturer's recommended stiffness category based on their weight, an RSP that is one category softer (k-) and an RSP that is one category stiffer (k+) than the manufacturer's recommended stiffness. We will measure ground reaction forces, metabolic demand, socket pressures, and socket pistoning while subjects run at the speed required for their age/sex 50th percentile PFT (Physical Fitness Test) 2 mile run and at 3 m/s, a total of six trials. If the data warrant it, we may add an additional stiffness category to further fine tune the optimal stiffness. The optimal stiffness (k_{opt}) distance-running RSP will be the RSP that minimizes metabolic cost. This RSP stiffness will be used for Day DR2.

 $\underline{\text{Day DR2:}}$ We will keep RSP stiffness constant (k_{opt}) and vary the distance-running RSP height (h). Subjects will have used an RSP with an optimal stiffness (k_{opt}) at the recommended height (h_R) on day Day DR1. On Day DR2, they will also use and RSP with an optimal stiffness (k_{opt}) that is 2 cm shorter (h-), and 2 cm taller (h+). We will measure ground reaction forces, metabolic demand, socket pressures, and socket pistoning while they run at their PTF speed and at 3 m/s; a total of four trials. If the data warrant it, we may further fine tune RSP height in 1 cm increments. We will analyze the results of DR2 to identify the optimal height (h_{opt}) for each subject for one brand of a distance-running RSP.

Days DR3 and DR5: We will repeat the trials of Day DR1 and vary stiffness (k) for a different distance-running RSP brand. We will analyze the results of Days DR3 and DR5 to identify the optimal RSP stiffness (k_{opt}) to be used for Days DR4 and DR6.

Days DR4 and DR6: We will repeat the trials of Day DR2 and vary height (h) for a different distance-running RSP brand. We will analyze the results of Days DR4 and DR6 to identify the optimal height (hoot) for each subject using the respective brand of a distance-running RSP.

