Specific Aim 2. Subjects will complete six experimental sessions at the University of Colorado Locomotion Laboratory; each session on a separate day and requiring approximately two hours of time. During each experimental session, subjects will run and sprint over a range of speeds, from 3 m/s up to top speed on a force measuring treadmill while we measure their ground reaction forces, socket pressures, and socket pistoning. Subjects will run with three different brands (Ossur, Ottobock, and Freedom Innovations) of sprint-running RSPs with at least three different stiffnesses at one height and three different heights at one stiffness of each brand, a total of five or more different conditions per brand. Individual trials at each speed will be approximately 15-30 seconds long with at least 2 minutes rest between trials.

A safety harness attached to the ceiling above the treadmill and handrails beside the treadmill will be used during all running/sprinting trials to ensure subjects' safety. Each running trial will consist of at least 10 strides. To begin each trial, subjects will lower themselves from the handrails on to the moving treadmill belt. For each prosthetic stiffness and height condition, subjects will start a series of trials at 3 m/s, each subsequent trial will be incremented by 1 m/s until subjects approach their top speed, and then smaller speed increments will be employed until subjects reach their top speed. *Top speed* will be determined when subjects put forth maximal effort but cannot maintain their position on the treadmill for ten strides (Weyand, Sternlight, Bellizzi, & Wright, 2000). Subjects will be given as much time between trials as needed to recover fully (at least 2 minutes). At least seven trials will be performed by each subject for each prosthetic condition (e.g. 3, 4, 5, 6,

7, 7.3, 7.5 m/s) and a maximum of three series of trials will be performed each day. Our results will allow us to determine the optimal RSP mechanical stiffness (k_{opt}) and height (h_{opt}) for each person. The optimal sprint-running (SR) RSP will be the prosthesis that maximizes top speed.

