In Specific Aim 1, we propose to have subjects complete a total of six running trials per day and each trial will last 5 minutes. In Specific Aim 2, we propose to have subjects complete three sets of running and sprinting trials from 3 m/s up to top speed and each trial will last approximately 30 seconds. The proposed experimental trials may be too difficult, long, and/or exhausting. However, we have previously conducted up to eight running economy trials without detecting any effects of fatigue (Grabowski & Kram, 2008; Teunissen, Grabowski, & Kram, 2007). Moreover, our previous studies of Paralympic athletes with transtibial amputations suggest that subjects can complete three sets of running and sprinting trials from 3 m/s up to top speed without showing effects of fatigue (Grabowski et al., 2010). Thus, we believe that our proposed experimental protocol will be adequate; however if we do see signs of fatigue, we may need to spread out the protocol over more days.

We expect to find that for some subjects the optimal stiffness is either softer or stiffer than the manufacturer's recommended stiffness or that the optimal height is taller or shorter that the traditionally recommended height. Therefore, it may be necessary to add conditions to our protocol so that we can establish the true minimum metabolic cost or maximum speed. On Days 2, 4, and 6, we would be able to test an additional stiffness and height condition without exceeding the recommended number of trials per session. If additional trials are necessary, we may need to add an additional day to our protocol.

F. Data Analysis Plan:

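### Data-triggered extra stiffness and height settings enter the group averages and the ANOVA as ordinary conditions, which biases their group contrasts in their favour if only some subjects receive them

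*Combined protocol and SAP*

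**What the plan says.** Every subject is scheduled for three stiffness categories at one height (softer, recommended, stiffer), then three heights at the chosen stiffness, for each brand (section IV.C, Days DR1 to DR6 and SR1 to SR6). Beyond that schedule the plan is open. For stiffness: "If the data warrant it, we may add an additional stiffness category to further fine tune the optimal stiffness" (Day DR1; the same sentence stands under SR1). For height: "If the data warrant it, we may further fine tune RSP height in 1 cm increments" (Day DR2; the same under SR2). No trigger is given, and nothing says whether an added setting goes to one subject or to all.

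Section IV.E gives the motive: "We expect to find that for some subjects the optimal stiffness is either softer or stiffer than the manufacturer's recommended stiffness", with a parallel statement for height. It concludes that "it may be necessary to add conditions to our protocol so that we can establish the true minimum metabolic cost or maximum speed".

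The optimum is defined per subject and on an analysed outcome. In Aim 1 the optimal-stiffness "distance-running RSP will be the RSP that minimizes metabolic cost". In Aim 2, "The optimal sprint-running (SR) RSP will be the prosthesis that maximizes top speed". Metabolic cost and top speed are both in the list of analysed variables.

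The analysis text at the start of section IV.C takes group averages for each condition and states: "We will use repeated measures analysis of variance (ANOVA) to compare each variable across all conditions". It does not set added settings apart. Its only provision for unequal numbers is to change the follow-up procedure to Scheffé's.

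**The concern.** If a subject moves on to a further setting because the outermost scheduled one was that subject's best, the further setting is observed only in subjects who respond in that direction. Its group average is then set beside averages over all 15 subjects, and the ANOVA tests it as though it were a condition like the others.

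The Scheffé switch deals with multiplicity, not with who was observed. A subject term removes differences in overall level, but selection here is on the subject's response to stiffness, so that term does not remove it either.

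At stake is the group-level statement about settings further from the recommendation. Such a setting can look nearly as good as the recommended one, although it would be clearly worse on average if everyone had tried it.

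**Working it through.** **Counts.** 3 stiffnesses + 3 heights - 1 shared setting = 5 conditions per brand, which matches the plan's minimum of five. The plan counts five or more per brand, so added settings are treated as conditions. It gives no effect size, SD or power figure to reproduce.

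**Assumed model.** Let x be the category relative to the recommended one, and m the subject's own optimum, m ~ N(0, s²). Cost = subject level + (x - m)² + noise. One unit is the cost of being one category off one's own optimum. The values of s and of the noise SD are assumptions. The settings -1, 0 and +1 are run in everyone, and +2 is added only if +1 was the subject's best.

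**True contrast, +2 minus recommended.** (2 - m)² - m² = 4 - 4m. Over all subjects the mean of m is 0, so the contrast is +4.0 (worse).

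**Selected contrast without noise.** Setting +1 is best when (1 - m)² < m², that is, m > 0.5. Among triggered subjects the mean optimum is M = s·φ(0.5/s) / [1 - Φ(0.5/s)].
- Paired, within recipients: 4 - 4M.
- Raw, recipients' average at +2 minus the all-subject average at recommended: 4 - 4M + (s² + 0.5M) - s² = 4 - 3.5M.
- s = 0.5: M = 0.5 × 0.242/0.159 = 0.763. Paired +0.95, raw +1.33.
- s = 1: M = 0.352/0.309 = 1.141. Paired -0.56, raw +0.01. About 31% of subjects are triggered.

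**With noise** (simulation). The last column is a subject-plus-condition ANOVA fit in trials of 15 subjects; a dash means not run.

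| SD of optima | Noise SD | Paired | Raw averages | ANOVA fit |
|---|---|---|---|---|
| 0.5 | 0 | +0.95 | +1.33 | - |
| 0.5 | 0.5 | +1.42 | +1.89 | +1.67 |
| 0.5 | 1 | +1.70 | +2.38 | about +2.3 |
| 0.5 | 2 | +1.81 | +2.92 | - |
| 1 | 0 | -0.56 | +0.01 | - |
| 1 | 0.5 | -0.39 | +0.22 | -0.27 |
| 1 | 1 | -0.23 | +0.50 | +0.15 |
| 1 | 2 | -0.04 | +1.07 | - |
| 1.5 | 1 | -1.97 | -1.04 | -1.72 |

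The true value in every row is +4.0. At SD 1 the ANOVA contrast was significantly negative in about 2% of simulated trials; at SD 1.5 with noise 1, in about 12%.

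**Limiting cases.** If all subjects share one optimum (noise 1), the raw average is unbiased (+3.99) and the paired contrast is +3.21. If stiffness has no effect at all, the paired contrast among recipients is still about -0.42 noise SD, while the raw and ANOVA estimates are about 0.

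**Height.** Assume SD of optima 2 cm, curvature 0.25 per cm², noise 1, and an extra height given if +2 cm was best. At +3 cm a true +2.25 shows as -1.01 in recipients. At +1 cm, inside the scheduled range, a true +0.25 shows as -1.08.

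**Complete cases.** If each subject gets at most one extra category, and some go softer while others go stiffer, nobody has every condition. An ANOVA that needs complete data would then keep 0 of 15. Extras in both directions arose within a brand in more than 90% of simulated trials.

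**The case against.** The strongest reply is that the plan never states the selective rule. It says only that settings may be added, and section IV.E speaks of adding conditions, or a day, to the protocol, which could mean for everyone. If so, the selection disappears. That stands as a limit: the selective use is inferred from the reference to some subjects and from optima defined per person.

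Second, both hypotheses concern the optimum for each subject, and extras serve that search. This also stands. The search is not harmed by this mechanism, nor are contrasts among the three scheduled stiffness categories.

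Third, a reader might infer that these group averages feed the prescription guidelines directly. The documents do not say so. Section IV.G bases its algorithms on weight, amputation level, limb segment lengths and desired speed, and does not say that condition means are used.

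Fourth, a reader might infer that the sign of the effect will reverse. That depends on an assumed spread. At SD 0.5 every estimate stays positive, and at SD 1 the raw averages that the plan names do not reverse.

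Fifth, it would be too strong to say that no group result for extras can be interpreted. If the trigger depends only on observed outcomes, a likelihood-based model using all the data can recover the contrast. With 15 subjects such a model averaged +4.06, +4.10 and +4.02 against a true +4.0 (SD of optima/noise SD: 1/0.5, 1/1 and 0.5/1).

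None of this rescues the analysis as written, which enters added settings as ordinary conditions and offers only a change of follow-up test.

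**Conclusion.** The concern holds conditionally. If extra settings are given to some subjects on the strength of their own metabolic cost or top speed, the stated group averages and ANOVA give a biased contrast for those settings, in their favour. Under the quadratic model a true +4.0 falls to about +1 to +3 at SD 0.5 category and to about -0.6 to +1.1 at SD 1, depending on the estimator and noise. Reversal on average in every estimator needs a wider spread, such as SD 1.5.

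The usual consequence is therefore a penalty that is understated or lost, not a significant result in the wrong direction. The size rests on assumed curvature, spread, noise and trigger, none of which the documents give. The direction is more robust, although the raw averages are essentially unbiased when optima do not vary. The problem arises only if the option to add settings is used.

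**What to change.** In the analysis text of section IV.C:
- Limit the group averages and the repeated-measures ANOVA for stiffness to the three categories that every subject receives. Likewise, do not enter data-triggered extra heights as group conditions.
- Use extra settings to choose the subject's own optimal stiffness or height. Report them descriptively, with the number of subjects and the trigger.
- State who receives extras. If they are meant for everyone, say so.
- If a group estimate for extras is wanted, fit a likelihood-based mixed model with stiffness (or height) as a continuous quadratic and a random subject slope. Fit it to all data, including those that triggered the extra setting.

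The cost is a sentence or two and no new data. The downside is that extra settings get no simple ANOVA p-value.

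This does not cure a separate selection in the height comparison. The recommended-height result at the optimal stiffness is carried over from the day on which that stiffness was chosen as best, so it is itself selected on the outcome and needs its own remedy.

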Day SR0: Subjects will be asked to give informed written consent and then will be fit and aligned by a certified prosthetist with three different sprint-running RSP brands, one from each company. We will measure each subject's height, weight, and limb segment lengths. Then, we will select an RSP stiffness category based on the subject's weight and manufacturer's recommendation. An appropriate RSP height for each subject will be chosen according to conventional practice. Our prosthetist will ensure that the prosthetic fit and alignment are adequate. Then, subjects will have time to accommodate to treadmill running and sprinting with each sprintrunning RSP over a range of speeds.

Day SR1: We will first vary the sprint-running RSP stiffness (k) while keeping height (h) at the recommended level. Subjects will use an RSP with the manufacturer's recommended stiffness category based on their weight, an RSP that is one category softer (k-) and an RSP that is one category stiffer (k+) than the manufacturer's recommended stiffness. We will measure ground reaction forces, top speed, socket pressures, and socket pistoning while subjects run and sprint over a range of speeds from 3 m/s up to their top speed. If the data warrant it, we may add an additional stiffness category to further fine tune the optimal stiffness. The optimal stiffness (k_{opt}) sprint-running RSP will be the RSP that maximizes top speed. This RSP stiffness will be used for Day SR2.

Day SR2: We will keep RSP stiffness constant (k_{opt}) and vary the sprint-running RSP height (h). Subjects will have used an RSP with an optimal stiffness (k_{opt}) at the recommended height (h_R) on day Day SR1. On Day SR2, they will also use and RSP with an optimal stiffness (k_{opt}) that is 2 cm shorter (h-), and 2 cm taller (h+). We will measure ground reaction forces, top speed, socket pressures, and socket pistoning while they run across a range of speeds from 3 m/s up to their top speed. If the data warrant it, we may further fine tune RSP height in 1 cm increments. We will analyze the results of SR2 to identify the optimal height (h_{opt}) for each subject for one brand of a sprint-running RSP

Days SR3 and SR5: We will repeat the trials of Day SR1 and vary stiffness (k) for a different sprint-running RSP brand. We will analyze the results of Days SR3 and SR5 to identify the optimal RSP stiffness (k_{opt}) to be used for Days SR4 and SR6.

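### Height days lack a same-day reading at the recommended height, so h_R against h-/h+ is confounded with day and, on the outcome that chose k_opt, tilted towards h_R; a cheap change removes both

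*Combined protocol and SAP*

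**What the plan says.** All references are to the combined protocol and SAP.

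- **Stiffness day (section IV.C, Day DR1).** Three stiffnesses are run at h_R and two speeds, six trials in all. "The optimal stiffness (k_{opt}) distance-running RSP will be the RSP that minimizes metabolic cost".
- **Height day (Day DR2).** Only h- and h+ are listed, with four trials. For h_R the text says: "Subjects will have used an RSP with an optimal stiffness (k_{opt}) at the recommended height (h_R) on day Day DR1". Then: "We will analyze the results of DR2 to identify the optimal height (h_{opt}) for each subject". No deciding outcome is named there.
- **Conditions (IV.C, Specific Aim 1).** Three stiffnesses at one height and three heights at one stiffness make "a total of five or more different conditions per brand at two speeds". Sessions are on separate days.
- **Aim 2 (IV.C, Specific Aim 2 and Day SR2).** The scheme is the same: "Subjects will have used an RSP with an optimal stiffness (k_{opt}) at the recommended height (h_R) on day Day SR1". Here the criterion is stated: "The optimal sprint-running (SR) RSP will be the prosthesis that maximizes top speed". Each day is capped: "a maximum of three series of trials will be performed each day".
- **Other brands.** DR4/DR6 and SR4/SR6 repeat the height-day scheme.
- **Options.** On the stiffness day: "If the data warrant it, we may add an additional stiffness category to further fine tune the optimal stiffness". Section IV.E says the height days have room for an extra stiffness and height condition, and that a further day may be added.

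No section plans a repeat of h_R on the height day, a day term in the analysis, or a correction for selection.

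**The concern.** The height comparison needs three readings at k_opt. Two are fresh and share a day. The third, h_R, comes from an earlier day and is the reading that won the stiffness contest.

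1. **Day.** Anything that differs between the two sessions goes into h_R versus h-/h+, whatever the outcome. The contrast of h- with h+ is same-day and unaffected.
2. **Selection.** The winner of three noisy readings is on average better than its own true value. On the outcome that picked it, h_R therefore starts with an advantage.

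The best height per subject and brand is a stated result of both aims. Section IV.D promises each subject a recommendation, and section IV.G builds prescription algorithms on these data. Section IV.E expects that for some subjects the best height is not the recommended one. The selection tilt works against finding those subjects.

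**Working it through.** **Step 1: the plan's own counts.** DR1: 3 stiffnesses x 2 speeds = 6 trials, as stated. DR2: 2 heights x 2 speeds = 4 trials, as stated; re-running h_R would make 6. Conditions per brand: 3 + 3 - 1 shared = 5, as stated. The counts fit only if h_R is not repeated.

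**Step 2: day, on an outcome with no selection.** The documents give no noise or day SD, so let sigma be the SD of one reading. As an illustration (the plan does not specify this test), take a paired t-test of h_R against the mean of h- and h+, at the plan's 5% level.

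- Variance of the difference, no subject-day variation: sigma^2 x (1 + 1/2) = 1.5 sigma^2.
- With an independent subject-day SD of 1 sigma on each day: 1.5 + 1 + 1 = 3.5 sigma^2.
- Non-centrality for a systematic shift of 0.5 sigma: 0.5 x sqrt(n) / sqrt(variance).

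| | n = 15 (all subjects in an aim) | n = 10 (unilateral) |
|---|---|---|
| Variance 1.5 | 1.58, rejects 31% | 1.29, rejects 21% |
| Variance 3.5 | 1.04, rejects 16% | 0.85, rejects 12% |

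With zero-mean subject-day effects and no systematic shift, the test rejects in 5%: noise is added, but no group bias.

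**Step 3: selection, on the outcome that chose k_opt.** Assumptions: normal noise with SD sigma, one score per condition (Aim 1 gives no rule for combining its two speeds), three stiffnesses with true values of SD tau, and no day effect. The expected maximum of three standard normals is 0.846, so the mean advantage of the carried-over h_R is 0.846 x sigma^2 / sqrt(sigma^2 + tau^2). The percentages come from simulation: k_opt is the best observed stiffness, h_R is that same reading, and h-/h+ are fresh readings at k_opt.

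| tau / sigma | 0 | 1 | 2 | 4 | h_R same day |
|---|---|---|---|---|---|
| Advantage of h_R (sigma) | 0.85 | 0.60 | 0.38 | 0.21 | 0 |
| No height effect: h_R named | 60% | 51% | 44% | 39% | 33% |
| h+ better by 1 sigma: h+ found | 49% | 54% | 58% | 60% | 63% |
| h+ better by 1 sigma: h_R named | 38% | 32% | 26% | 23% | 18% |
| h_R better by 1 sigma: h_R found | 88% | 80% | 74% | 69% | 63% |

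At tau = 0 the 60% is exact: h_R holds three of five exchangeable readings, 3/5.

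**Step 4: net accuracy, 1 sigma lead, no day shift.** If each height is equally likely to be best, correct picks are (h_R found + 2 x h+ found) / 3.

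- tau = 0: (87.6 + 2 x 49.4) / 3 = 62.1%, against 63.4% with a same-day h_R, a loss of 1.3 points.
- The loss shrinks as tau grows and is close to zero at tau = 4 sigma.

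The carry-over breaks even when h_R is truly best in a share P of subjects, P = (63.4 - h+ found) / (h_R found - h+ found).

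- tau = 0: (63.4 - 49.4) / (87.6 - 49.4) = 14.0 / 38.2 = 37%.
- tau = 4 sigma: (63.4 - 60.3) / (69.3 - 60.3) = 3.1 / 9.0 = 34%.

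**Step 5: both together, tau = 1 sigma, no height effect.** If the height day is better by 0.6 sigma, h_R is named in 32% and the tilt is cancelled. If it is worse by 0.5 sigma, h_R is named in 67%. Only the selection part has a known direction.

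**The case against.** **Carry-over is not an explicit rule.** Read literally, the best height comes from the height day's results alone, which would leave h_R out of the choice. The three heights per brand, the wording that subjects will *also* use h- and h+, and the trial and condition counts make carry-over the better reading. The text needs fixing on either reading.

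**A large day shift is not shown.** This stands. Subjects need at least one year of RSP experience, and DR0/SR0 provide fitting and accommodation. These make a large systematic shift less likely but do not remove day effects. A model term does not rescue the comparison either: with session as a factor, h_R versus h- is not estimable. A linear trend could be separated if all brand orders were used, but no brand order is stated.

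**The tilt may help.** h_R is the conventional choice. If it is truly best in more than about 34-37% of subjects (1 sigma lead, no day shift), carry-over gives more correct picks. This stands too, so a reader who infers a large loss of accuracy goes further than the figures allow. What remains is that the plan would name h_R too often for the subjects whose best height lies elsewhere.

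**Aim 1.** A reader might infer that both aims share the selection fault. Day DR2 names no criterion. Section IV.E points to metabolic cost, but Hypothesis 1 also lists asymmetry and socket limits. If those help to decide, the fault shrinks, and for a criterion with independent error it vanishes.

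**Inflated type I error.** A reader might also infer a badly inflated error rate in a height ANOVA. Section IV.C specifies an ANOVA across all conditions, not a separate test of three heights, so no such figure belongs to this plan.

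**Conclusion.** The point holds as a cheap improvement to the height days. The day confounding applies to h_R versus h-/h+ on every outcome, with one exception: if an optional fourth stiffness is run on the height day and wins, its h_R reading is same-day, though still selected. The documents do not size a day shift. The selection tilt follows from the stated criterion in Aim 2 and is conditional in Aim 1. Its size depends on assumed SDs: it is clear when true stiffness differences are small against trial noise and modest when they are large. It is a directional tilt against non-standard heights, not a general failure of the selection rule. A day shift could enlarge, cancel or reverse it.

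**What to change.** On Days DR2/4/6 and SR2/4/6, run the k_opt RSP at all three heights and decide from that day's data. Possible text: *On height days subjects will use the k_opt RSP at h-, h_R and h+ in random order; h_opt and all height comparisons will use these same-day data only.* If a fourth stiffness is tested, settle k_opt before the height trials. This removes the tilt and the day confounding whichever criterion decides h_opt.

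**Cost, Aim 1.** Height days go from four to six trials, the DR1 load. Trials plus minimum rests go from 4 x 5 + 3 x 2 = 26 minutes to 6 x 5 + 5 x 2 = 40, or 3 x 14 = 42 minutes more per subject.

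**Cost, Aim 2.** Height days go from two series to three, the stated maximum. At seven trials of 15-30 seconds per series with two-minute rests, that is about 30-33 minutes rising to 45-51.

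Both fit the planned two-hour session and need no extra subjects or equipment. The change uses the spare height-day slot described in section IV.E, so optional fine-tuning may need the additional day foreseen there. Brand comparisons remain across days.
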